Derivation of the PI and percent change in MED at 10 minutes, 1 hour, and 24 hours time points will be performed using precise MED_{baseline} values at the corresponding time point and derivation at 48 hours and 72 hours timepoints will be performed using the precise MED_{baseline} at 24-hour time point.

MED values reported as "> X" on eCRF will be converted to X for the purpose of statistical data analysis, but will be presented as recorded, i.e. as "> X" in the listings.

15.2. PRIMARY ANALYSIS OF PHOTOSENSITIVITY

The objective of this trial is to investigate the photosensitivity under three distinct exposure conditions of BI 730357 following 8 days of administration (i.e. at steady state) on the basis of the primary and secondary endpoints. The trial is designed to allow comparisons between BI 730357 and placebo as well as BI 730357 and a positive control (ciprofloxacin) for each of 2 dose cohorts (400 mg QD and 300 mg BID) separately. These comparisons will be evaluated statistically for each dose cohort separately by use of a mixed model for repeated measures (MMRM). The analysis of primary, secondary and further endpoints will be based on the FAS.

The photosensitivity index (PI) under conditions 1 and 2 is the measurement used for the primary endpoints. It is defined as the ratio of the precise MED_{baseline} to the MED_{on-drug} at each respective post-irradiation timepoint. Therefore, there will be MED_{baseline} at 10 min, 1h, and 24h that will be used for the respective PI calculations, PI_{10min}, PI_{1h}, and PI_{24h}. For example, the PI_{1h} will be the precise MED_{baseline}/MED_{on-drug} where each MED was measured at the 1 hour post-irradiation time point. The two primary endpoints are PI at 24 hours under conditions 1 and 2.

For each dose cohort separately, a MMRM (with unstructured [UN] covariance) on PI values will be utilized for the primary analysis. The model will include treatment (BI 730357 and Placebo from the respective dose cohort, Ciprofloxacin), time (10min, 1h, 24h, 48h, and 72h), and treatment-time interaction as fixed effects and subject as a random effect. Adjusted means and differences in PI and 90% CIs for the 2 contrasts of interest (i.e. BI 703357 – placebo at 24h) will be calculated from the model.

The ANOVA model is described by the following equation:

$$y_{ijk} = \mu + \tau_i + d_{ij} + \theta_k + (\tau\theta)_{ik} + e_{ijk}, \text{ where}$$

y_{ijk} = PI response measured at time k on subject j receiving treatment i,

μ = the overall mean,

Document: L:\BIOS\Boehringer_Ingelheim_Pharmaceuticals\BI730357\1407-0037_MZA56588\Biostatistics\Documentation\SAP

Author: [REDACTED] Version Number: Final V2.0
Version Date: 23JUL2020

Template No: CS_TP_BS016 – Revision 5
Effective Date: 01Apr2018

Reference: CS_WI_BS005

τ_i = the i-th treatment effect, $i = 1, 2, 3$,

d_{ij} = the random effect associated with the j-th subject receiving treatment i,

θ_k = the k-th time effect, $k = 1, 2, 3, 4, 5$, and

e_{ijk} = the random error associated with the j-th subject receiving treatment i at time k,

where $d_{ij} \sim MVN(0, \sigma_1^2 I)$ and $e_{ijk} \sim MVN(0, \sigma_2^2 I)$; MVN=multivariate normal.

The SAS code for fitting the above ANOVA model will be similar to:

PROC MIXED ;

 CLASS treatment subject time ;

 MODEL PI=treatment time treatment*time/DDFM=KR ;

 REPEATED time / subject(treatment) type=un;

 ESTIMATE statements to obtain point estimates and the corresponding 90%, 95% CIs for contrasts of interest;

 RUN ;

For each dose cohort, the analysis will be carried out separately for Condition 1 and Condition 2.

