7.1 NULL AND ALTERNATIVE HYPOTHESES

BI 730357 vs placebo

The assessment for absence of photosensitivity will be based upon the differences in mean photosensitivity index (PI) between BI 730357 and placebo two-sided 90% confidence intervals (CIs) for the differences in the photosensitivity index (Section 7.2.2) between BI 730357 and placebo using an acceptance range of -0.4 to 0.4. This method is equivalent to the two-sided t-test procedure, each at the 5% significance level.

The following comparisons will be performed:

- BI 730357 400 mg QD vs placebo 400 mg QD
- BI 730357 300 mg BID vs placebo 300 mg BID

The following hypotheses are tested:

Null hypothesis H₀ (Photosensitive): $\mu_{BI} - \mu_{pbo} \le -\delta \ or \ \mu_{BI} - \mu_{pbo} \ge \delta$

Where μ_{BI} and μ_{pbo} are the means of the endpoint for BI 730357 and placebo, respectively, and δ is the limit that defines the acceptance range for photosensitivity equivalence.

Alternative hypothesis H_a (Absence of photsensitivity): $-\delta < \mu_{BI} - \mu_{pbo} < \delta$

In this trial, the equivalence limit δ is 0.4 which is consistent with historical criteria used for positive photosensitivity for a drug (R19-3037).

The rejection of the null hypothesis at the $\alpha = 0.05$ level is equivalent to the inclusion of the 90% confidence interval for μ_{BI} - μ_{pbo} in the acceptance range (- δ , δ).

Although there are multiple endpoints where the photosensitivity index will be statistically compared, an alpha adjustment is not needed because it is required that all endpoints meet the equivalence criterion as described above simultaneously.

c27983101-03 Clinical Trial Protocol Page 63 of 79

Proprietary confidential information © 2020 Boehringer Ingelheim International GmbH or one or more of its affiliated companies

BI 730357 vs ciprofloxacin, Placebo vs ciprofloxacin

Comparisons between the mean PI between BI 730357 and ciprofloxacin as well as between placebo and ciprofloxacin at the different timepoints under conditions 1 and 2 will be performed.

The planned comparisons are:

- BI 730357 400 mg QD vs ciprofloxicin
- BI 730357 300 mg BID vs ciprofloxicin
- Placebo for 400 mg QD vs ciprofloxicin
- Placebo for 300 mg BID vs ciprofloxicin

At each timepoint the null hypothesis will be that there is no difference in the mean PI of BI 730357 compared to ciprofloxacin:

Null hypothesis H_0 : $\mu_{BI/pbo} - \mu_{cipro} = 0$

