7.5 DETERMINATION OF SAMPLE SIZE

It is planned to include initially a total of 84 healthy male and female subjects (36 subjects for Treatment A 400 mg QD, 36 subject for Treatment A 300 mg BID; 12 subjects for Treatment B) in this trial.

The planned numbers of subjects should be sufficient for the exploratory evaluation of photosafety of each of the BI 730357 dose groups. Based on a similarly designed study for evaluation of pradigastat the observed mean (standard deviation) over all PI measurements for 9 patients who received placebo and 12 subjects who received ciprofloxacin was 1.08 (0.12) and 1.61 (0.55), respectively (R19-3037).

Assuming a common standard deviation of 0.15 and an expected difference in mean PI of 0 between BI 730357 and placebo, each of the two group 0.05 one-sided t-tests will have 99% power to reject the null hypothesis that BI 730357 and placebo are not equivalent (the difference in means, μ_{BI} - μ_{pbo} , is \geq 0.4 and μ_{BI} - $\mu_{pbo} \leq$ -0.4) in favor of the alternative hypothesis that the means of the two groups are equivalent (nQuery Advisor, version 7).

Additionally, for the planned comparison of mean PIs for BI 730357 and ciprofloicin, a two group Satterthwaite t-test with a 0.05 two-sided significance level will have 87% power to detect a difference in means of 0.6 (the difference between μ_{cipro} of 1.60 and a μ_{BI} of 1.0) assuming standard deviation of ciprofloxacin is 0.600 and standard deviation for BI 730357 is 0.15 when the sample sizes in the two groups are 12 and 27, respectively (nQuery Advisor, version 7). Using the same assumptions and calculation for 12 ciprofloxacin and 9 placebo instead of 27 BI 370357 subjects the power is 86%. Based on the similar study of pradigastat, the drop-out rate will be minimal. Further details will be discussed in the TSAP.

c27983101-03 Clinical Trial Protocol Page 68 of 79

Proprietary confidential information © 2020 Boehringer Ingelheim International GmbH or one or more of its affiliated companies

8. INFORMED CONSENT, TRIAL RECORDS, DATA PROTECTION, PUBLICATION POLICY, AND ADMINISTRATIVE STRUCTURE

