The alternative hypothesis will be that the means are not equal:

Alternative hypothesis H_a : $\mu_{\text{BI/pbo}} - \mu_{\text{cipro}} \neq 0$

A significant finding of increased photosensitivity of ciprofloxacin compared to BI 730357 400 mg QD and to placebo QD at the $p<0.05$ level will be supportive in concluding that the trial was appropriately designed to test the photosensitivity of BI 730357 400 mg QD.

15.3.2. 300 MG BID Dose Cohort

For comparisons of BI 730357 300 mg BID vs placebo BID, BI 730357 300 mg BID vs ciprofloxacin, and placebo BID vs ciprofloxacin, null and alternative hypotheses will be identical to the respective null and alternative hypotheses described above for the 400 mg QD dose cohort.

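### SAP 15.2 gives all three arms one common covariance although Protocol 7.5 plans a ciprofloxacin SD four times that of BI 730357 and placebo: the primary CI becomes about 2.1 times too wide and the ciprofloxacin CIs too narrow

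*SAP*

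**What the plan says.** SAP 15.2 describes one model per dose cohort, run separately for each condition: "The model will include treatment (BI 730357 and Placebo from the respective dose cohort, Ciprofloxacin" (the same three arms are listed in Protocol 7.2.2). The text asks for an unstructured covariance, and also for "treatment-time interaction as fixed effects and subject as a random effect". The SAS code has "REPEATED time / subject(treatment) type=un", with no GROUP= option and no RANDOM statement. The written equation has one subject variance and one error variance, neither indexed by treatment. Either way, the three arms share the same variance.

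The sample-size section works differently. Protocol 7.5 takes a common SD of 0.15 for BI and placebo. For ciprofloxacin it proceeds by "assuming standard deviation of ciprofloxacin is 0.600 and standard deviation for BI 730357 is 0.15", and states that a "two group Satterthwaite t-test with a 0.05 two-sided significance level will have 87% power to detect a difference in means of 0.6". The source figures, SD 0.12 for placebo and 0.55 for ciprofloxacin, are "the observed mean (standard deviation) over all PI measurements for 9 patients who received placebo and 12 subjects who received ciprofloxacin".

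In the text available, SAP section 15 contains no unequal-variance analysis and no sensitivity analysis for unequal spread.

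**The concern.** The sponsor planned for a 4:1 SD ratio and then specified an analysis that assumes 1:1. With a shared covariance and complete data, each 24 h contrast is a pooled-variance comparison on 27 + 9 + 12 - 3 = 45 df. The 12 ciprofloxacin subjects would then inflate the error variance of the BI-placebo contrast, to which they contribute no information. The two low-variance arms would deflate the error variance of the ciprofloxacin contrasts.

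For the primary test the stake is precision. A modest true difference well inside the 0.4 margin could miss equivalence because the positive control is variable. Protocol 7.1 also says "it is required that all endpoints meet the equivalence criterion as described above simultaneously", so the loss compounds over the two conditions.

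For ciprofloxacin the stake is over-optimistic CIs and p-values. Those comparisons are secondary evidence, but a significant result "will be supportive in concluding that the trial was appropriately designed to test the photosensitivity of BI 730357 400 mg QD". The same ciprofloxacin group serves both cohorts (SAP 15), so both analyses are affected.

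Separately, the equation (random subject effect plus independent errors, which is compound symmetry) is not the model in the text and code (unstructured). Two programmers could fit different models.

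**Working it through.** **Inputs.** n = 27 BI and 9 placebo per cohort (Protocol 3.2) and 12 ciprofloxacin; SDs 0.15, 0.15 and 0.60; ciprofloxacin shift 0.6 (all Protocol 7.5); margin 0.4 with a two-sided 90% CI (SAP 15.3.1, 15.4). Complete data are assumed.

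**Protocol figures reproduced.** Two one-sided tests at n 27/9, SD 0.15, true difference 0: power above 99.9% (stated 99%). Satterthwaite test, difference 0.6: 87.8% for 12 vs 27 (stated 87%) and 86.7% for 12 vs 9 (stated 86%).

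**Pooled SD under the SAP model.**

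sqrt[(26×0.0225 + 8×0.0225 + 11×0.36)/45] = sqrt(4.725/45) = 0.324, against 0.15 from BI and placebo alone. Ciprofloxacin supplies 3.96 of the 4.725, or 84%.

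**Primary 90% CI half-width**, t × SD × sqrt(1/27 + 1/9):
- three arms, 45 df: 1.679 × 0.324 × 0.385 = 0.209
- two arms, 34 df: 1.691 × 0.15 × 0.385 = 0.098

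The ratio is 2.15. Averaged over simulated trials the half-widths are 0.206 and 0.097, ratio 2.13. With 24/8/11 subjects the formula gives 2.16.

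**Ciprofloxacin 95% CI half-width.**
- vs BI: pooled SE 0.324 × sqrt(1/27 + 1/12) = 0.112, half-width 0.226. Unequal-variance SE sqrt(0.36/12 + 0.0225/27) = 0.176 on 11.6 df, half-width 0.384.
- vs placebo: pooled SE 0.143, half-width 0.288. Unequal-variance SE 0.180 on 12.8 df, half-width 0.390.

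Simulated means are 0.223 vs 0.376 and 0.283 vs 0.383.

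**Operating characteristics** (400,000 simulated trials per scenario, normal data). The three-arm 90% CI covers the true BI-placebo difference 99.8% of the time. Probability of concluding equivalence in one condition:

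| True difference | Three-arm | Two-arm |
|---|---|---|
| 0 | 99.4% | >99.9% |
| 0.05 | 98% | >99.9% |
| 0.10 | 91% | >99.9% |
| 0.15 | 74% | 99.5% |
| 0.20 | 47% | 96% |
| 0.40 (false conclusion) | 0.1% | 5.0% |

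With a true difference of 0.20 in both conditions, the joint probability lies between 0.467² = 22% (independent) and 47% (fully correlated). The two-arm range is 0.960² = 92% to 96%.

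The ciprofloxacin 95% CIs cover 78% (vs BI) and 87% (vs placebo). If the larger SD persisted without any mean shift, single-test type I error would be 21.6% and 13.0%. Both tests would reject in the required direction in 5.9% of trials, against 1.8% with Satterthwaite.

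**Range over the unknown ciprofloxacin SD** (BI and placebo at 0.15, except the last row):

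| Ciprofloxacin SD | CI ratio | Equivalence at 0.20, three-arm | Type I vs BI / placebo | Both, required direction |
|---|---|---|---|---|
| 0.60 | 2.13 | 47% | 21.6% / 13.0% | 5.9% |
| 0.45 | 1.70 | 71% | 19% / 12% | 4.9% |
| 0.30 | 1.31 | 89% | 14% / 9% | 3.0% |
| 0.20 | 1.08 | 95% | 8% / 6% | 1.3% |
| 0.15 | 1.00 | 96% | 5% / 5% | 0.5% |
| 0.55, others 0.12 | 2.39 | 60% (two-arm 99.5%) | 22% / 13% | 6.4% |

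**The case against.** The strongest reply is that no planned operating characteristic fails. Protocol 7.5 plans a true difference of 0 and 99% power, and the SAP model still gives 99.4%. False equivalence drops below its nominal level, which is the safe direction in a photosafety trial. The losses arise at true differences that the protocol does not anticipate. All of this stands, and it limits the seriousness of the point. It does not justify letting another drug's spread set most of the width of the main result.

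The SD ratio at 24 h within one condition is unknown, because the source SDs cover all measurements. This stands too, so every figure is conditional. SAP 15.1 also writes PI inverted, as on-drug over baseline. On that scale a delta-method conversion gives SDs of about 0.15 and 0.60/1.6² = 0.23, and a CI ratio of about 1.15. Protocol 5.1 and 7.2.2 and SAP 15.2 all define PI as baseline over on-drug, the scale of the planning SDs, so the larger ratio is the relevant one for PI. The secondary percent change in MED is on the inverse scale and would be less affected.

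The figures assume the unstructured model. Compound symmetry would also pool over time points and change the exact ratio, but would still share one variance across arms.

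The ciprofloxacin type I errors require a large SD with no mean shift, whereas in the cited study the large SD came with a raised mean. The criterion also needs both tests to succeed in one direction, which would happen falsely in only 5.9% of trials. That is fair for the testing claim. The poor CI coverage does not depend on the shift.

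Descriptive SDs by treatment are planned, so unequal spread would be visible. Seeing it would not correct the intervals.

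**Conclusion.** The concern holds and should be fixed. Under the sponsor's own planning SDs, with near-complete data and the unstructured model, the primary 90% CI is conservative and about 2.1 times too wide. The ciprofloxacin 95% CIs are about 0.59 (vs BI) and 0.74 (vs placebo) of their proper width. The primary conclusion is not at greater risk of being falsely reassuring, and power at a true difference of 0 is intact. The loss matters at true differences of roughly 0.10 to 0.20. The effect shrinks to a ratio of 1.31 at a ciprofloxacin SD of 0.30 and vanishes with equal SDs. The mismatch between equation and code is a defect whatever the SDs turn out to be.

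**What to change.** 1. Estimate the primary BI-placebo contrast from the same repeated-measures model fitted only to that cohort's BI and placebo arms.
2. For the ciprofloxacin contrasts, use the Satterthwaite t-test at each time point, as Protocol 7.5 already assumes. A two-level variance group (ciprofloxacin vs Part A) is an alternative. In simulation at a single time point both hold single-test type I error at 5.0% to 5.2% for ciprofloxacin SDs of 0.15 to 0.60. The two-level version needs 2×15 = 30 covariance parameters, including a 5×5 matrix from 12 subjects, and its convergence has not been tested, so Satterthwaite is the safer default. Avoid a separate unstructured matrix per treatment: 3×15 = 45 parameters, with one matrix from 9 placebo subjects whose MEDs are read on 25% dose steps.
3. Make the equation match the code: unstructured covariance, with the subject effect written as subject=subject(treatment).
4. Declare the change in SAP 3.3, because Protocol 7.2.2 and the synopsis prespecify the three-arm model.

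The cost is SAP text and a few lines of code. The primary contrast has 34 instead of 45 df, which loses almost nothing if the SDs are equal (96.0% vs 96.1% at a true difference of 0.20). The chance that ciprofloxacin beats both BI and placebo at the planned shift of 0.6 falls from 95% to 85%, in line with the 87% and 86% per test in Protocol 7.5.

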15.3. NULL AND ALTERNATIVE HYPOTHESES

15.3.1. 400 MG QD Dose Cohort

BI 730357 400 mg QD vs Placebo QD

The assessment for absence of photosensitivity will be based upon the differences in mean photosensitivity index (PI) between BI 730357 400 mg QD and placebo QD two-sided 90% confidence intervals (CIs) for the differences in the photosensitivity index between BI 730357 400 mg QD and placebo QD using an acceptance range of -0.4 to 0.4. This method is equivalent to the two-sided t-test procedure, each at the 5% significance level.

The following hypotheses will be tested:

Null hypothesis H_0 (Photosensitive): $\mu_{BI} - \mu_{pbo} \leq -\delta$ or $\mu_{BI} - \mu_{pbo} \geq \delta$

Where μ_{BI} and μ_{pbo} are the means of the endpoint for BI 730357 400 mg QD and placebo QD, respectively, and δ is the limit that defines the acceptance range for photosensitivity equivalence.

Alternative hypothesis H_a (Absence of photosensitivity): $-\delta < \mu_{BI} - \mu_{pbo} < \delta$

In this trial, the equivalence limit δ is 0.4 which is consistent with historical criteria used for positive photosensitivity for a drug [1].

The rejection of the null hypothesis at the $\alpha = 0.05$ level is equivalent to the inclusion of the 90% confidence interval for $\mu_{BI} - \mu_{pbo}$ in the acceptance range $(-\delta, \delta)$.

Document: L:\BIOS\Boehringer_Ingelheim_Pharmaceuticals\BI730357\1407-0037_MZA56588\Biostatistics\Documentation\SAP

Author: [REDACTED] Version Number: Final V2.0
Version Date: 23JUL2020

Template No: CS_TP_BS016 – Revision 5
Effective Date: 01Apr2018

Reference: CS_WI_BS005

Although there are multiple endpoints where the photosensitivity index will be statistically compared, an alpha adjustment is not needed because it is required that all endpoints meet the equivalence criterion as described above simultaneously.

BI 730357 400 mg QD vs ciprofloxacin, Placebo QD vs ciprofloxacin

Comparisons between the mean PI between BI 730357 400 mg QD and ciprofloxacin as well as between placebo QD and ciprofloxacin at the different timepoints under conditions 1 and 2 will be performed.

At each timepoint the null hypothesis will be that there is no difference in the mean PI of BI 730357 400 mg QD compared to ciprofloxacin:

Null hypothesis H_0 : $\mu_{\text{BI/pbo}} - \mu_{\text{cipro}} = 0$

Where $\mu_{\text{BI/pbo}}$ and μ_{cipro} are the means of the endpoint for BI 730357 400 mg QD or placebo QD and ciprofloxacin, respectively.

The alternative hypothesis will be that the means are not equal:

Alternative hypothesis H_a : $\mu_{\text{BI/pbo}} - \mu_{\text{cipro}} \neq 0$

A significant finding of increased photosensitivity of ciprofloxacin compared to BI 730357 400 mg QD and to placebo QD at the $p<0.05$ level will be supportive in concluding that the trial was appropriately designed to test the photosensitivity of BI 730357 400 mg QD.

15.3.2. 300 MG BID Dose Cohort

For comparisons of BI 730357 300 mg BID vs placebo BID, BI 730357 300 mg BID vs ciprofloxacin, and placebo BID vs ciprofloxacin, null and alternative hypotheses will be identical to the respective null and alternative hypotheses described above for the 400 mg QD dose cohort.

15.4. PRIMARY ENDPOINT ANALYSIS OF PHOTOSENSITIVITY INDEX

400 mg QD Dose Cohort:

The primary analysis will be based on FAS for both conditions 1 and 2 at the 24 hour assessment.

Least squares (LS) mean for the difference between BI 730357 400 mg QD and placebo QD along with the corresponding 2-sided 90% CI will be obtained from the MMRM described in Section 15.2 above.

Absence of photosensitivity between BI 730357 400 mg QD and placebo QD will be concluded if the 2-sided 90% CI is fully contained within the acceptance range (-0.4, 0.4).

A significant finding of increased photosensitivity of ciprofloxacin compared to BI 730357 400 mg QD and to placebo QD at the $p<0.05$ level will be supportive in concluding that the trial was appropriately designed to test the photosensitivity of BI 730357 400 mg QD.

Document: L:\BIOS\Boehringer_Ingelheim_Pharmaceuticals\BI730357\1407-0037_MZA56588\Biostatistics\Documentation\SAP

Author: [REDACTED] Version Number: Final V2.0
Version Date: 23JUL2020

Template No: CS_TP_BS016 – Revision 5
Effective Date: 01Apr2018

Reference: CS_WI_BS005

Additionally, descriptive statistics by treatment will be provided for the primary endpoints.

For Conditions 1 and 2, figures of LS mean PI (+/- standard error [SE]) versus time points will be provided.

300 mg BID Dose Cohort:

The primary endpoint analysis of PI for the 300 mg BID dose cohort will be identical to that described above for the 400 mg QD dose cohort. Comparisons of BI 730357 300 mg BID vs placebo BID, BI 730357 300 mg BID vs ciprofloxacin, and placebo BID vs ciprofloxacin will be performed.

15.5. SECONDARY ENDPOINT ANALYSES

400 mg QD Dose Cohort:

The secondary endpoints for differences in PI at 10 minutes and 1 hour under Conditions 1 and 2 will be calculated from the same MMRM model as described for the primary analyses.

Additionally, percent change from baseline in MED at 10 minutes, 1 hour, and 24 hours will be analyzed at each timepoint using the same MMRM model described in the primary analysis.

LS means along with corresponding 95% CIs and p-values for the difference between BI 730357 400 mg QD and placebo QD; between BI 730357 400 mg QD and ciprofloxacin; and between placebo QD and ciprofloxacin will be obtained from the MMRM described in Section 15.2 above.

For Conditions 1 and 2, figures of LS mean % change (+/- SE) versus time points will be provided.

Additionally, descriptive statistics by treatment will be provided for the secondary endpoints.

300 mg BID Dose Cohort:

The secondary endpoint analyses for the 300 mg BID dose cohort will be identical to those described above for the 400 mg QD dose cohort. Comparisons of BI 730357 300 mg BID vs placebo BID, BI 730357 300 mg BID vs ciprofloxacin, and placebo BID vs ciprofloxacin will be performed.

Document: L:\BIOS\Boehringer_Ingelheim_Pharmaceuticals\BI730357\1407-0037_MZA56588\Biostatistics\Documentation\SAP

Author:

Version Number:

Final V2.0

Version Date:

23JUL2020

Template No: CS_TP_BS016 – Revision 5
Effective Date: 01Apr2018

Reference: CS_WI_BS005

